# Protocol

## 3.3. Rationale for current study

The aim is to develop a new treatment for a common, serious and currently untreatable condition. We propose a definitive study of the efficacy of peanut oral immunotherapy (OIT) as a treatment for peanut allergy. Immunological mechanisms will be studied. We have conducted a pilot which demonstrated proof of concept; the present study includes larger numbers and a control group, with power to detect outcome at the 0.05 significance level. There will be two inter-dependent work packages (figure 1). Package 1 will be a randomized comparison of intervention versus the current best management. Package 2 will confirm efficacy in the waiting list group when subsequently treated and allow an estimate of the overall success rate to within 10%.

#### 3.3.1 Recruitment

This is a single centre study. The intervention is complex and requires intensive clinical input; therefore a single centre with concentrated expertise makes more efficient use of resources than a multi-centre design. We can be confident of recruiting families from a broad geographical region. Following the recent national media publicity resulting from our pilot study, we received many enquiries from families across the UK, with peanut allergic children (the prevalence of peanut allergy is 2% in childhood). We are aware that this may result in participation bias with more motivated families with a vested interest in enrolling. The concern is that we recruit a sample of highly motivated individuals who show excellent compliance with treatment, which may not be representative of the response we might see from a more general sample recruited in our own clinic. We will therefore widen recruitment and include patients directly from our allergy clinic (we regularly review over 1500 peanut/nut allergic children in our clinic). We will perform a pre-planned sub group comparison of compliance and outcome between the national and locally recruited groups.

#### 3.3.2 Expected natural resolution and success of therapy based on pilot results

For the power calculation, we have estimated the proportion of participants in the control group whom we expect to have undergone spontaneous resolution of their peanut allergy after a fivemonth waiting list control period. The current best estimate of spontaneous resolution is that it occurs in up to 20%, although this is in children with mild allergy, and occurs over a longer period. On current data, in the patients we are recruiting one would expect a resolution rate considerably below 20%. We have taken a conservative estimate of a 30% rate of natural resolution. For the success rate in the actively treated group we have used a conservative estimate of 64%. In our pilot study, 10/11 (91%) children who have completed peanut immunotherapy became completely tolerant to peanut and one tolerated 10 rather than 12 peanuts. The study has 90% power to detect a difference of 64% v 30% at the 0.05 significance level (see para10 for full details).

#### 3.3.3 Peanut allergy diagnosis

It is vital to the study that the diagnosis is confirmed at the outset before group allocation, as determination of trial success depends on robust case definition. Therefore we will use the research gold-standard for diagnosis of active peanut allergy (DBPCFC) in all participants. The challenge is performed according to international consensus guidelines. This challenge will also identify the threshold for reactivity (minimum amount of peanut required to cause a reaction) that will be used during minimization for group allocation. At the outset we expect all participants to have active peanut allergy, therefore for safety reasons the challenge commences at a low dose (1-100mg). Only participants with a positive DBPCFC will be included in the study.

#### 3.3.4 Group allocation

Within an individual various factors including severity of allergy (from history and challenge), age, presence of asthma, and other active allergies, are known to influence reactivity and thus may influence the successful response to immunotherapy. Random group allocation may result in an imbalance of these factors between the active and control groups, leading to bias. To account for this, subjects will be allocated using minimization, with a random element using a weighting probability of 0.8.

## 3.3.5 Active intervention and control group Peanut oral immunotherapy

Participants randomized to the active intervention arm will receive daily doses of peanut protein with two-weekly increments (see section 7). Participants will undergo six-seven months of immunotherapy before a second peanut challenge. Dose increments were well tolerated in our pilot study (achieved in 16/16) with no serious adverse events.

#### Control group

We have added a control group. There are no data on resolution in severe peanut allergy. The allergy may resolve in up to 20% of mildly peanut allergic children. This is thought to happen slowly over a number of years, rather than the relatively short period of our study. The control group will undergo peanut avoidance for five months (current practice) during which time they are on the 'waiting list' before receiving active intervention. A recent study demonstrates precedent of using a waiting list control group: 45 children with egg and cow's milk allergy were randomised to waiting list control or oral immunotherapy. After 18-24 months all control group subjects had a positive food challenge, demonstrating persistence of their allergy. Subjects randomized to the control group will receive the current best management (peanut avoidance management plan) for six-seven months [in pilot duration was 58-210d (median 143d, mean 140d; about 5 months) n=12;]. This is provided using verbal and written information provision and training in the use of emergency medication and provision of an emergency treatment plan. In an ideal world, we would administer a placebo to participants in our control arm and this was considered in great detail during development work. The main reason for not including a placebo is the impossibility of being able to adequately blind an active or placebo snack. Importantly, in our open design pilot study 70% of children had reactions immediately after taking an active dose, meaning participating families (and the investigators) would quickly work out which arm of the study they were on. After development work, we also concluded that it was not possible to adequately mask larger doses of peanut protein in a snack size acceptable for a child to eat every day (800mg is the equivalent of 5-7 peanuts). An alternative would be to provide a peanut-flavored placebo snack, but it would be unethical to leave families on either arm in doubt as to whether oral tolerance had been induced or not. Families who falsely assume they are on the active treatment arm may relax their allergen avoidance practice, thereby putting their child at increased risk of a reaction. We feel that a placebo arm would also hamper recruitment and compliance. The obvious disadvantage of not including a placebo snack is that subjects will know which study arm they are assigned to. This is offset by the fact that the primary outcome (peanut allergy) will be diagnosed on the basis of an objective measure: double blind, placebo-controlled food challenge (DBPCFC), the gold-standard for food allergy diagnosis in research. On peanut challenge, neither the investigator, the nurse, nor the participant will know whether the participant's dose is peanut or placebo, so it will be impossible for the outcome of the challenge to be influenced by that knowledge.

After completion of the second DBPCFC we will offer active immunotherapy to those in the waiting list control group who still have a diagnosis of peanut allergy. This is intended to maintain the high ethical standard of the study and encourage robust recruitment and compliance. We do not feel it is acceptable to families to wait for six months and attend for two peanut challenges, with their attendant risks, without a chance of receiving an active therapy. This will also to combine data from two active intervention groups to improve statistical power.

#### 3.3.6 Severity

The Board has asked us to consider whether it would be appropriate to perform this study on a lower risk group. Arguably, those with the most to gain from this treatment are those at greatest risk of a severe reaction in the community. These include older children, those with low thresholds or a history of severe reactions, and those with asthma. We believe for the intervention in this study to be translated into a useful clinical treatment, studies must include these high-risk groups. Our pilot study included subjects with allergies of all severity represented. We demonstrated that it is possible to safely induce tolerance in subjects who have previously suffered an anaphylactic peanut reaction, those with very low documented thresholds for reactivity and those with asthma, so we have not excluded these individuals from participating.

#### 3.3.7 Future development

The current proposal will advise on efficacy, mechanism and safety, also showing persistence of effect in the short to medium term. We are committed to future study that will investigate the optimal duration of maintenance treatment for long-term tolerance. In other forms of immunotherapy a maintenance treatment period of several years is required to induce a 'permanent' cure. This study is likely to catalyze and boost healthcare development for related allergic diseases. Not only will it provide a clinical treatment for peanut allergy, addressing a potentially life-threatening allergy in up to 2% of the childhood population, but it will also stimulate development of immunotherapy for other potentially severe food allergies e.g. tree nuts, sesame, fish, lupin and severe egg and milk allergy. We are currently experiencing an expansion in new food allergies: kiwi, mustard, lupin, fruits etc. The current study will provide a model for studying desensitization for novel food allergies as they emerge. Further no expensive vaccine is required. We have designed this intervention using cheap materials so that the treatment can be replicated at minimal cost and made widely available.

#### 3.3.8 Outcome measure

The main goal of this trial is to compare the proportion of participants with peanut allergy after immunotherapy versus peanut avoidance. Therefore the outcome measure must be robust and objective.

We will be applying double blind placebo controlled peanut challenges to subjects in both groups.

#### 3.3.9 Immunological Assessments (mechanism)

The state of the art is that it is known that clinical tolerance during natural resolution or immunotherapy to inhaled allergens is accompanied by several immunological changes. Results from small studies of different parameters for food allergy indicate early changes such as recruitment of regulatory T cells (producing IL-10) or production of specific IgG antibodies, mid term changes including reversal of the ratio of allergy-skewed T helper cells and late changes such as reduction in specific IgE. Changes in histamine receptor expression have recently been noted during bee venom immunotherapy. However, there has not been a single longitudinal or more comprehensive examination of these features in food allergy immunotherapy, in comparison with a control group. A key difficulty in providing immunotherapy is knowing when a permanent cure has been effected and active treatment can be stopped. Current clinical biomarkers e.g. serum specific IgE or skin prick tests remain positive long after successful inhalant immunotherapy. As a result the duration of immunotherapy is probably overestimated. Definition of a surrogate marker would be of great clinical value in individualising treatment. A further important clinical question is defining in which group of patients immunotherapy is likely to be tolerated and successful, identifying such a biomarker will streamline provision of care in the future.

This clinical trial of oral tolerance induction will be accompanied by a series of studies that will permit us to identify the following:

- Longitudinal characterisation of early, mid and late-term molecular mechanisms associated with the development of oral tolerance during peanut immunotherapy
- Biomarkers that may identify the achievement of tolerance to peanut in individuals

- Indicators of an active (immunomodulatory) response to oral tolerance induction during successful therapy.
- Biomarkers to help predict a positive outcome for oral tolerance induction

Our strategy for identifying these biomarkers and indicators will involve longitudinal comparisons of immune-response profiles over time within individuals, as tolerance is achieved (or when it is unsuccessful). We will also compare immune-response profiles between individuals on the control arm and those on the active intervention arms. Qualitative, quantitative, and time-dependent changes in allergen immune-response profiles of participants who do or do not develop tolerance to peanut will provide data for testing current hypotheses and generating new hypotheses to explain underlying tolerogenesis mechanisms. To identify the biomarkers associated with underlying tolerance mechanisms in operation at the time of sampling, we will perform analysis of the immune-response profiles at enrolment and at 14 days (early-point), 75 days (mid-point) and 150 days (latepoint) after active intervention or avoidance. Integration of biological responses with clinical outcomes will provide a means to identify the potential biomarkers outlined above. Assays at these time points for all subjects will include:

•Total and crude peanut-specific IgE, peanut-specific IgG and IgG4

•Ara h 1-3, 8 and 9-specific IgE, IgG and IgG4 will be measured

Peanut specific T helper cell proliferation and cytokine response (supernatant IL-4/IFN gamma and IL-10 by ELISA; intracellular IL-4, IFN gamma and IL-10 by flow cytometry)

In a subset of older subjects able to provide a larger blood volume (200mls; >14yrs) we plan :

- Isolation of basophils and assay of activation markers CD63 and CD203c measured by flow cytometry during peanut allergen stimulation.
- Ratio of histamine HR1 to HR2 receptor mRNA on basophils by semi-quantitative polymerase chain reaction

Specimens may also be used in future immune response or biomarker assays to re-evaluate biological response as research tests are developed.

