#### 5. Research design

**5.1 Design.** This is a randomized controlled trial of a novel active intervention (peanut oral immunotherapy) versus the status quo (peanut avoidance) in 104 participants (7-18yrs) with peanut allergy (figure 1). One hundred and four participants will be recruited and undergo characterization by history, allergy testing, blinded peanut challenge and quality of life questionnaire. Peanut allergy will be confirmed in all participants by DBPCFC. Subjects are then allocated to either active or control group. Central minimization with weighting will be used to account for variation in severity of reaction (from history and challenge), peanut threshold dose (from challenge), age, sex, asthma, and allergies to other foods. After six-seven months subjects will undergo a DBPCFC (primary outcome measure). Subjects in the control group will receive current best management (a comprehensive management plan focusing on peanut avoidance) for six-seven months followed by DBPCFC. Those in the control group who still have a diagnosis of peanut allergy will be invited to undertake peanut oral immunotherapy followed by a final peanut challenge.

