#### 7.1 Peanut oral immunotherapy

Subjects randomized to the active intervention arm will receive daily doses of peanut protein starting at 1mg per day. This is given as peanut flour (50% protein) and is mixed into a carrier which is known to be tolerated (e.g. yoghurt). The first dose is administered on the Clinical Research Ward (CRW) followed by a 2 hour observation period. Subsequently this dose is taken daily at home by participants. Every 2 weeks subjects return to the CRW for a dose increase and 1 hour of observation. The dose increments are 1, 5, 12, 25, 50, 100, 200, 400 and 800mg. The final dose (or if this is not tolerated, the highest tolerated dose) is taken for at least six weeks until six-seven months post randomization when a DBPCFC is performed.

Provide each participating family with:

- Symptom advice sheet (containing advice to avoid strenuous exercise for 2 hours after home dose)
- Contact information (explain 24 hour contact system)
- Non-sedating oral antihistamine and injectable adrenaline device
- Training on adrenaline autoinjector use (provide trainer pen)

- Emergency treatment plan
- Subjects are asked to complete a symptom diary, noting type and duration of symptoms and any exacerbating factors (e.g. exercise, excessive tiredness, systemic illness).

If symptoms are experienced during updosing on the Clinical Research Ward then do the following:

- If wheeze / breathlessness / reduced PEFR / vomiting occur then provide the next lowest dose for daily active intervention. It should be noted that this action was not required in the pilot study. If the dose causing the reaction was the starting dose (1mg), then provide 0.5mg peanut protein for daily active intervention. Contact daily to reassess.
- If mild abdominal pain, oral itching or urticaria occurs then provide reassurance and continue the current dose. Contact daily to reassess
- If other symptoms occur that are intolerable to the subject that the dose can also be reduced at the investigator's discretion.

If any symptoms are experienced by participants at home, families are advised to contact the study team. Serious adverse events will be handled separately as below in section 9.

Make the following assessments and provide advice as indicated:

- If wheeze / breathlessness / vomiting occurs within 2 hours of a single dose taken at home then reduce the dose to the next lowest, and contact daily to reassess

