#### 9.1.1 Challenge timing

All participants will undergo a DBPCFC at enrolment (we expect the majority to react during this) After six-seven months the active and control group subjects undergo a second DBPCFC. The control group will then undergo immunotherapy, after six-seven months they also undergo a final DBPCFC.

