#### 11.2 Endpoint analysis

**11.2.1 Analysis of primary endpoint**: The main analysis will compare the proportion of subjects who pass a peanut challenge in the intervention and control arms six-seven months after randomization, using a Fisher's exact test at the p<0.05 level of significance.

**11.2.2 Analysis of secondary endpoints**. Quality of life scores will be compared before and after intervention by pair wise comparison within individuals, and group medians will be compared using methods for non-parametric data. The results of cellular and humoral assessments of immune responses will be compared using methods for non-parametric data (e.g. comparison of medians of serum peanut specific IgG4 at different time points by Mann-Whitney U test). The incidence of adverse events will be compared between the intervention and control groups using a two-tailed Fisher's exact test at the p<0.05 level of significance. For package 2, the proportion of patients who may expect success will be calculated, with 95% confidence intervals. The influence of severity, age, sex, other allergy on immunotherapy success will be assessed by multiple logistic regression analysis.

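### The late immune sample at day 150 fits the older five-month schedule, not the six-seven month challenge, so it falls about 33 to 63 days before tolerance is tested

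*Protocol*

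**What the plan says.** Section 3.3.9 of the Protocol takes immune profiles at enrolment, at an early point on day 14, and at "75 days (mid-point) and 150 days (latepoint) after active intervention or avoidance". Among the aims these samples serve, it lists "Biomarkers that may identify the achievement of tolerance to peanut in individuals" and, as a separate item, markers that help predict a good outcome. It plans to combine the immune results with the clinical outcome.

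The clinical outcome is the second blinded challenge:

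- Section 5.1: "After six-seven months subjects will undergo a DBPCFC (primary outcome measure".
- Section 7.1, active arm: the final dose "is taken for at least six weeks until six-seven months post randomization when a DBPCFC is performed".
- Section 9.1.1: "After six-seven months the active and control group subjects undergo a second DBPCFC".
- Section 11.2.1 compares the proportions who "pass a peanut challenge in the intervention and control arms six-seven months after randomization".
- Section 8.1 says six months, the lower end of that range.

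A shorter schedule also survives. Section 3.3.2 gives a five-month control period. Section 3.3.5 gives controls five months in one sentence and six-seven months in another. The avoidance advice at the end of section 7.1 has controls avoiding peanut for five months until the repeat challenge.

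In Table 2 the 150-day draw is the last blood-sampling milestone. No text shown schedules an immune sample at the outcome challenge.

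**The concern.** A marker of achieved tolerance has to be measured close to the time when tolerance is shown to be present or absent. On the six-seven month schedule, the sample called late is taken while active-arm children have one to two further months of daily dosing ahead of them. Immune change in that interval goes unobserved. Section 3.3.9 itself names a fall in specific IgE as a late change, which an early cut-off is the most likely to miss. A day-150 result related to pass or fail then behaves more like a predictor than a marker of the achieved state, and the two aims become hard to tell apart.

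A statistical analysis plan cannot repair this. Sampling days are fixed in the Protocol, and a sample that was not drawn cannot be recovered.

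**Working it through.** **Inputs.** Last sample: day 150 (section 3.3.9). Challenge: six to seven months (sections 5.1, 7.1, 9.1.1, 11.2.1). Alternative: five months (sections 3.3.2, 3.3.5, 7.1). Dosing: nine levels, hence eight two-weekly increases, then at least six weeks on the final dose (section 7.1).

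**Assumptions.** One month is 365.25/12 = 30.44 days. Day 150 is counted from the start of intervention or avoidance, and that start is taken as the day of randomization. If dosing starts d days after randomization, the active-arm gaps below shrink by d days.

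**Gap between last sample and challenge** = challenge day − 150.

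| Challenge at | Day | Gap (days) |
|---|---|---|
| 5 months | 152.2 | 2.2 |
| 6 months | 182.6 | 32.6 |
| 7 months | 213.1 | 63.1 |

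With 30-day months, the six-seven month gap is 30 to 60 days. Day 150 therefore matches the five-month schedule almost exactly and misses the other by one to two months.

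**Time on the top dose in the active arm, fastest schedule.**

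- 800mg is first reached at 8 × 14 = day 112.
- Six weeks on it ends at 112 + 42 = day 154.
- Time at 800mg at the late sample: 150 − 112 = 38 days at most.
- Time at 800mg at the challenge: 182.6 − 112 = 71 days to 213.1 − 112 = 101 days.

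Even the fastest child has had 38 days at 800mg when sampled, against 71 to 101 when tested.

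**Mixed case.** If the five-month sentence in section 7.1 governs controls and the six-seven month text governs the active arm, the interval from sample to challenge is about 2 days in controls and 33 to 63 days in the active arm.

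**Reading of the time origin.** The sampling days could be read as counted from the end of the intervention. An early point at day 14 and the parallel with avoidance make the start the natural origin.

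**The case against.** The strongest reply is that the Protocol carries two durations and that day 150 is consistent with one of them. That stands. It makes the mismatch look like a date left over from a five-month design, and it rules out a flat claim that no child has a sample near the challenge: for controls under the section 7.1 advice, the sample and the challenge coincide.

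Other replies also limit the point:

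- Most of the immunology is served by fixed common days. Section 3.3.9 plans comparisons over time within children and between arms, and section 4 asks for change over time. A sample before the challenge suits the prediction aim. A reader might infer that the biomarker endpoint is defeated; the text does not support that, because the serial samples can still be related to pass or fail.
- Section 3.3.9 speaks of mechanisms operating when a sample is taken. That wording does not itself require a sample at the challenge.
- The 38 days at 800mg fall only four days short of the six-week minimum. The contrast with 71 to 101 days at the challenge is the more relevant one.
- A reader might infer that many children are still up-dosing at day 150. Three delayed steps would move 800mg to 112 + 3 × 14 = day 154, but that child is hypothetical. Section 3.3.5 reports increments achieved in 16 of 16 pilot children, so the documents give no basis for a sizeable fraction.

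Table 2 gives one date for completing the third challenges and the 150-day sampling. These are project completion dates, so they do not show that the two coincide within a child.

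**Conclusion.** The mismatch is real and is best described as a sampling day that agrees with the five-month text and not with the six-seven month text. On the six-seven month schedule, the last immune sample precedes the deciding challenge by about 33 to 63 days, after at most 38 days at 800mg. One of the four aims in section 3.3.9, markers of achieved tolerance, is poorly served; prediction and longitudinal description are less affected. The primary endpoint, its Fisher's exact test and the sample size are untouched.

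The conclusion rests on counting from the start of intervention, on that start being close to randomization, and on no challenge-linked immune draw appearing in Figure 1 or in the Protocol pages that are not shown. It deserves correction because the change is cheap and the sample cannot be obtained later.

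**What to change.** 1. Reconcile the five-month wording (sections 3.3.2, 3.3.5 and the avoidance advice in 7.1) with the six-seven month wording (sections 3.3.5, 5.1, 7.1, 9.1.1 and 11.2.1). This has to come first, because a challenge-linked draw is at the same time in both arms only if the challenge is.
2. In section 3.3.9, redefine the late sample as a draw in the week before the second challenge, in both arms, and in the week before the third challenge for waiting-list children who were treated. It replaces the day-150 draw. Change the 150-day milestone in Table 2 to match.
3. Record the actual sampling day, and relate this sample to pass or fail.

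**Cost.** Protocol wording and a moved sample date. The number of samples and the blood volume do not change. Two downsides need handling. Sampling time will vary by about 30 days between children (213 − 183), which loosens the common-day comparison and is why the actual day should be recorded. The 200 ml draw planned in a subset of older participants must be scheduled apart from the challenge itself.
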